11 BLINDING/UNBLINDING

Since this is an open-label study, there will be no blind.

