10 CLINICAL EVALUATIONS

The following clinical evaluations will be performed according to the schedule indicated during the study. The same grader should conduct the efficacy assessments for a subject at all visits, to prevent variations in grading.

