10.1 Clinical Assessments

10.1.1 Investigator Assessments

Clinical efficacy assessments of the face will be performed as follows at all visits, unless otherwise specified. Whole numbers are allowed only (i.e. no half-points, or plus or minus designations).

Overall Photodamage (0-9 scale)

- None (0) = Facial skin is smooth to the touch, without significant fine/coarse lines or skin tone unevenness in any areas (periocular area, cheeks, forehead, and perioral area)
- Mild (1- 3) = Facial skin shows 1 area (periocular area, cheeks, forehead, and perioral area) of significant roughness, or skin tone unevenness (red/brown), or fine/coarse lines
- Moderate (4- 6) = Facial skin shows 2 areas (periocular area, cheeks, forehead, and perioral area) of significant roughness, skin tone unevenness (red/brown), or fine/coarse line
- Severe (7- 9) = Facial skin shows 3 or more areas (periocular area, cheeks, forehead, and perioral area) of significant roughness, skin tone unevenness (red/brown), or fine/coarse lines

Skin Roughness (0-4 scale)- Allergan Skin Roughness Visual Scale (Refer to Appendix I)

- None (0) = Smooth visual skin texture
- Minimal (1) = Slightly coarse and uneven visual skin texture
- Moderate (2) = Moderately coarse and uneven visual skin texture; may have early elastosis
- Severe (3) = Severely coarse visual skin texture, crosshatched fine lines; may have some elastosis
- Extreme (4) = Extremely coarse visual skin texture, crosshatched deep creases; extreme elastosis

Tactile Roughness (0-9 scale entire face)

- None (0) = No roughness of the treatment area; skin is completely smooth and pliable

- Mild (1-3) = Some areas of slightly irregular roughness in the treatment area
- Moderate (4-6) = Several areas of definite roughness of the treatment area
- Severe (7-9) = Marked roughness of the treatment area associated with stiff feeling

Fine Lines (0-4 scale) - Allergan Fine Lines Visual Scale (Appendix II)

- None (0) = No fine lines
- Minimal (1) = 1-2 superficial lines
- Moderate (2) = 3-5 superficial lines
- Severe (3) = Greater than 5 superficial lines; no crosshatching
- Diffuse (4) = Diffuse superficial lines; crosshatching

Fine Lines/Wrinkles - Forehead, Periocular, Cheeks, Perioral areas individually assessed (0-9 scale) (Refer to Appendix III)

- None (0) = No fine lines/wrinkles present; skin looks completely smooth and wrinkle-free
- Mild (1-3) = Rare, presence of fine lines and wrinkles, widely spaced apart in the treatment area

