- Moderate (4-6) = Moderate number of fine lines/wrinkles in close proximity to each other in the treatment area
- Severe (7-9) = Many fine lines/wrinkles densely packed together in the treatment area

Coarse Lines/Wrinkles - Forehead, Periocular, Cheeks, Perioral areas individually assessed (0-9 scale) (Refer to Appendix III)

- None (0) = No coarse lines/wrinkles present; skin looks completely smooth and wrinkle-free
- Mild (1-3) = Rare, presence of coarse lines and wrinkles, widely spaced apart in the treatment area
- Moderate (4-6) = Moderate number of coarse lines/wrinkles in close proximity to each other in the treatment area
- Severe (7-9) = Many coarse lines/wrinkles densely packed together in the treatment area

Global Improvement in Photodamage (0-4 scale; at follow-up visits only)

- None (0) = No change or worsening
- Mild (1) = A noticeable improvement of the condition with a distinctive amount of signs/symptoms remaining (approximately 25% overall improvement)
- Moderate (2) = A very noticeable improvement of the condition with a fair amount of signs/symptoms remaining (approximately 50% overall improvement)
- Marked (3) = A distinctive improvement of the condition with some signs/symptoms remaining (approximately 75% overall improvement)
- Complete (4) = Almost complete improvement of the condition with a trace of signs/symptoms remaining (approximately 95% or better overall improvement)

Global Improvement in Fine Lines/Wrinkles – Forehead, Periocular, Cheeks, Perioral areas individually assessed (0-4 scale; at follow-up visits only)

[figure not shown]
- None (0) = No change or worsening
- Mild (1) = Mild improvement in the appearance of fine lines/wrinkles (approximately 25% overall improvement)
- Moderate (2) = Moderate improvement in the appearance of fine lines/wrinkles (approximately 50% overall improvement)
- Marked (3) = Marked improvement in the appearance of fine lines/wrinkles (approximately 75% overall improvement)
- Complete (4) = Complete clearing in the appearance of fine lines/wrinkles (approximately 95% or better overall improvement)

Global Improvement in Coarse Lines/Wrinkles – Forehead, Periocular, Cheeks, Perioral areas individually assessed (0-4 scale; at follow-up visits only)

- None (0) = No change or worsening
- Mild (1) = Mild improvement in the appearance of coarse lines/wrinkles (approximately 25% overall improvement)

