10.1.3 Instrumentation

Standardized digital photography will be taken of the subject's left, right and frontal facial views with the [REDACTED]

Triplicate 3D images of a designated area on the face will be taken with the [REDACTED] at baseline and all follow-up visits.

Non-invasive *in vivo* skin imaging will be conducted with the [REDACTED] and [REDACTED] on a designated target area on the face at baseline and all follow-up visits.

Triplicate measurements of the facial skin at a target location will be taken using a [REDACTED] at baseline and all follow-up visits.

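### Section 11 gives up all masking because use is open-label, although stored 3D and in vivo images can still be read with the visit hidden

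*Combined protocol and SAP*

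**What the plan says.** - Section 11 (Blinding/Unblinding) consists of one sentence: "Since this is an open-label study, there will be no blind". It does not distinguish knowledge of the product from knowledge of the visit when an outcome is read.
- The Synopsis (Treatment Groups) gives every subject the test product after the wash-out. There is no control arm.
- Section 10 adds: "The same grader should conduct the efficacy assessments for a subject at all visits, to prevent variations in grading". Section 10.1.1 places the grading at the visits: "Clinical efficacy assessments of the face will be performed as follows at all visits, unless otherwise specified". The global improvement scores are given only after baseline. The live grader therefore knows the visit.
- Section 3 states the objective as assessing cosmetic change by means of skin imaging instruments.
- Section 10.1.3 schedules triplicate 3D images and in vivo imaging of a designated area at baseline and at every later visit. For photographs it says "Standardized digital photography will be taken of the subject's left, right and frontal facial views with the", and the sentence then runs into a redaction, so the photograph visits are not visible.
- Section 16.3 plans descriptive statistics. Section 16.1 reports no sample size calculation for this pilot.

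**The concern.** The step from open-label use to no masking at all does not follow. In a single-arm study everyone knows the product, but the person who outlines, measures or scores a stored image need not know whether it is from Baseline or Week 12.

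This matters more here than in a controlled trial. With two arms, an expectation that later visits look better would affect both arms and largely cancel in the comparison. Here it is added to the estimated change, and nothing in the data can separate it from a product effect. Section 2 describes prior studies showing improvement with retinol, so an expectation of benefit is plausible. The image-based changes are what the study exists to report, and Section 17.7 foresees publication.

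**Working it through.** The plan states no alpha, power, SD or sample size basis, so there is no figure to reproduce. The check has three parts.

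**1. How the key endpoints are read** (Synopsis, Study Endpoints)

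- Severity scores: overall photodamage 1, fine lines/wrinkles 4 areas, coarse lines/wrinkles 4 areas, tactile roughness 1, fine lines visual scale 1, skin roughness visual scale 1. Total 1 + 4 + 4 + 1 + 1 + 1 = 12.
- Global improvement scores: photodamage 1, fine lines 4, coarse lines 4, tactile roughness 1. Total 10.
- Instrument value: spectrophotometer L*, 1.
- Sum: 12 + 10 + 1 = 23, of which 12 + 10 = 22 are scores by an unmasked grader.

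**2. What could be masked**

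- 3D and in vivo images: taken at baseline and all later visits (Section 10.1.3), so the files can be coded. They cover only a designated area, so they cannot stand in for the four-area line scores.
- Photographs: they show the "left, right and frontal facial views" and could support the line and wrinkle severity scales: 4 fine + 4 coarse + 1 fine lines visual scale = 9. This holds only if Baseline and Week 12 photographs exist.
- Tactile roughness needs touch. The overall photodamage anchors in Section 10.1.1 also refer to touch and roughness.
- L*, if generated automatically, leaves little for an expectation to act on.

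**3. How much a visit-linked shift would matter (illustration)**

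Assumptions: n = 50 (Section 5 says approximately 50, the Synopsis up to 50), all with a change score, true mean change zero, approximately normal changes, and a shift b that follows visit order.

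- 95% half-width in SD units of the change: t(0.975, 49)/√50 = 2.010/7.071 = 0.284.
- With b = 0.284 SD, the noncentrality is 0.284 × 7.071 = 2.008. The noncentral t distribution with 49 df gives a probability of 0.50 that the interval excludes zero.
- With b = 0.40 SD the probability is 0.79; with 0.45 SD, 0.88; with no shift, 0.05.

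In scale points on a 0–9 score, by the normal approximation Φ(b√n/SD − 1.96) + Φ(−b√n/SD − 1.96), n = 50:

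| Assumed SD of change | b = 0.25 point | b = 0.5 point |
|---|---|---|
| 0.75 | 65% | 99.7% |
| 1.0 | 42% | 94% |
| 1.5 | 22% | 65% |

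For SD 1.0 and b = 0.25: 0.25 × 7.071/1.0 = 1.768, and Φ(−0.192) + Φ(−3.728) = 0.42. With the visit hidden, so that no shift can follow visit order, each entry returns to 5%.

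**The case against.** The strongest reply is that this is a declared open-label exploratory pilot with descriptive analysis. Section 11 contradicts nothing else in the protocol, and using one grader per subject is a reasonable control on between-grader variation. That is fair. It sets the weight of the point, but it does not explain why image files should be read unmasked.

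Several stronger readings are tempting, and the documents do not support them:

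- *That image analysts are known to see the visit.* This can only be inferred from Section 11. No visible text says who analyses the images or how far the output is automated, and the devices are redacted.
- *That Baseline and Week 12 photographs are certainly available.* The photograph visits are not visible.
- *That a bias of 0.28 SD is enough by itself to produce a false finding.* It does so in about half of trials, and the plan specifies no interval or test. The figure says nothing about the bias actually present.
- *That masked photographs could replace the live grades.* They show less than a live examination and cannot capture touch. A grader who saw the subject may remember the grades given. The mild redness and peeling expected under Section 6.2 could reveal the visit.
- *That masking would repair the global improvement scales.* How those scales are built is a separate matter, and a masked severity read leaves them unchanged.

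These limits narrow the remedy. They do not defend a blanket refusal of masking.

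**Conclusion.** The point holds as a low-cost improvement in design, not as an error that invalidates the study. The reason given in Section 11 does not apply to the reading of stored images. In a single-arm study this leaves the imaging results open to an expectation bias that could have been prevented.

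The count of 22 in 23 describes how exposed the visible key endpoints are to an unmasked grader. It is not the number that the fix would protect. Coding the 3D and in vivo files protects the image readings that serve the Section 3 objective. The optional photograph read would give masked support for 9 of the 22 scores, and the other 13 would remain live only.

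The size of the bias is unknown, and the percentages rest on assumed SDs and shifts with n = 50. Because the analysis is descriptive, the consequence is biased reported mean changes. The conclusion also assumes that the redacted text contains no masked read; such a read would conflict with Section 11 as written.

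**What to change.** **Main change.** Amend Section 11 to say that product use is open-label, but that any operator-dependent measurement or scoring of the 3D and in vivo images is made on files with subject and visit labels removed, presented in random order. State in Section 10.1.3 who reads the images. Fully automated values such as L* are unaffected. The cost is coding and shuffling files, with no new staff, visits or procedures.

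**Optional addition.** First confirm that photographs are taken at Baseline and Week 12. If so, an existing site grader, preferably not the one who graded that subject live, scores the visual line and wrinkle scales from coded photographs in random order. Report this as a supportive analysis beside the live grades. Overall photodamage and tactile roughness stay live. The cost is reader time for at most about 50 × 2 = 100 photograph sets. The report should state the limits: less detail than a live examination, and possible partial unmasking by redness or peeling.

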12 END OF STUDY

At the end of each subject's participation in the study, the investigator will complete an End of Study Form for all completed and discontinued subjects.

12.1 Completion of the Study

Subjects who complete all 5 visits will have completed the study.

12.2 Subject Discontinuation

A subject may be withdrawn from the study prior to completion for any of the following reasons:

- Whenever the subject/care giver decides it is in their best interest to withdraw
- Whenever the investigator decides it is in the subject's best interest to be withdrawn
- Severe adverse events
- Intercurrent illness which may, in the investigator's opinion, significantly affect assessment of clinical status
- Non-compliance
- Pregnancy

If a subject does withdraw prematurely from the study, all procedures required for their current or "last visit" plus any additional final study requirements should be completed.

Subjects who are prematurely withdrawn or discontinued from the study may be replaced.

12.3 Study Termination

The study may be terminated by the investigator or the Sponsor. If, in the opinion of the investigator, clinical observations made during the study, suggest that it may be unwise to continue, her or she may stop the study. A study termination by the investigator will be reported to the Sponsor.

In addition, a written statement fully documenting the reasons for this action will be submitted to the Sponsor by the investigator within five working days.

In the event that the Sponsor chooses to discontinue or terminate the study, appropriate notification will be given to the investigator.

13 ADVERSE EVENT REPORTING

13.1 Adverse Events

Any clinical findings determined by the Investigator to be important and/or unusual will be referred to as an adverse event (AE). Subjects are asked to contact the clinic staff immediately if they experience a reaction at any time during the study. The subject may be examined by the clinic's staff or by the study physician. The start of adverse event collection for this study will be immediately after the subject completes their Screening visit.

13.2 Definitions of Adverse Event and Serious Adverse Event

An adverse event is any untoward medical occurrence in a patient or a clinical investigational subject that is administered a medicinal product and which does not necessarily have to have a causal relationship with this treatment. An adverse event can therefore be any unfavorable and unintended sign (for example an abnormal laboratory finding), symptom, or disease temporally associated with the use of a medicinal product, whether or not considered related to this medicinal product. Throughout the study, subjects will be monitored for signs and symptoms of adverse events. The condition must either not be present pre-study or must worsen in either intensity or frequency during the study.

A *serious adverse event* (SAE) is an untoward medical occurrence that at any dose:

- results in death;
- is life-threatening (NOTE: The term "life-threatening" in the definition of "serious" refers to an event in which the patient was at risk of death at the time of the event; it does not refer to an event which hypothetically might have caused death if it were more severe.);
- requires in-patient hospitalization or prolongation of existing hospitalization;
- results in persistent or significant disability/incapacity;
- is a congenital anomaly/birth defect; or
- is an important medical event.

An *unexpected adverse event* is any treatment-emergent adverse event, which is not identified in nature, severity, or frequency in current literature on the Test Product.

13.3 Reporting Requirements

- **Serious and Unexpected Adverse Events**

Any serious, unexpected and treatment-related adverse event occurring in this study must be reported to [REDACTED] within 10 business days of awareness of the event using the Serious Adverse Event Report form [REDACTED]

- **Adverse Event Reporting**

All adverse events must be recorded by the Investigator onto the Adverse Event page of the source documents. The Investigator will be required to describe the adverse event, onset and stop date, severity, opinion of causality, the course of action taken, if any, as well as any pertinent data necessary to allow a complete evaluation of the adverse event. For serious adverse events, an additional report (SAE Report Form) must be completed. The completed Adverse Event CRF and the SAE Report Form must be emailed to SkinMedica Medical Affairs at [REDACTED] within 24 hours of awareness.

- **Follow-up and Final Reports**

Subjects who have had a serious adverse event must be followed clinically until all parameters, including laboratory values (if applicable), have either returned to baseline or are otherwise explained.

If death was the outcome of the event on the initial SAE Report, a Follow-up/Final Report, including autopsy report, when performed, must be completed.

References used:

- International Conference of Harmonization (ICH) Guidelines: <http://www.ich.org>
- E2A – Clinical Safety Data Management: Definitions and Standards for Expedited Reporting

Serious adverse events will be reported to the Sponsor within 24 hours (or the next working day). The main Sponsor contact for serious adverse events is:

The Investigator will follow-up the case to assess the cause, effect, and severity of any AE, and findings will be documented on an AE form. If medical expenses are incurred by the subject in conjunction with the study, they will be billed separately to the Sponsor. If a physician is engaged to participate in any observations beyond scheduled visits, his fees will be billed separately to the Sponsor.

13.4 Pregnancy

Sexually active women of child bearing potential (WOCBP) must use an effective method of birth control during the course of the study, in a manner such that risk of failure is minimized. Prior to study enrollment, WOCBP must be advised of the importance of avoiding pregnancy during trial participation and the potential risk factors for an unintentional pregnancy. The subject must sign an informed consent form documenting this discussion.

During the study, all WOCBP should be instructed to contact the investigator immediately if they suspect they might be pregnant (e.g., missed or late menstrual period).

14 CLINICAL SUPPLIES

14.1 Study Test Product

- SkinMedica Retinol Complex 0.5 [SkinMedica, Inc., an Allergan Company]

14.2 Study Basic Skincare Products

- SkinMedica Facial Cleanser [SkinMedica, Inc., an Allergan Company]
- Cetaphil Moisturizing Lotion [Galderma Laboratories, L.P.]
- SkinMedica Essential Defense Mineral Shield Broad Spectrum SPF 35 [SkinMedica, Inc., an Allergan Company]

14.3 Return and Destruction of Study Medication Supplies

Since all the products used in this study are commercially-available cosmetic and OTC products, the subjects will not be required to return any used and/or unused product.

15 SUBJECT COMPENSATION

Subjects who complete all of the required study visits will be compensated with SkinMedica products (up to \$527 retail value). Upon completion of the Baseline and Week 4 visits, subjects will be eligible to receive a credit for one SkinMedica TNS Essential Serum (\$281 retail value). To avoid noncompliance and use of the products during the study, these products will be provided at the final visit, regardless of study completion.

Upon completion of the Week 8 visit, subjects will be eligible to receive one SkinMedica HA5 (\$178 retail value) at their final Week 12 visit. At the Week 8 visit, subjects will be asked to select which SkinMedica products they would like to receive at their final (week 12) visit.

Upon completion of the Week 12 visit, subjects will be eligible to receive one SkinMedica sunscreen product (up to \$68 retail value) at their final Week 12 visit. At the Week 8 visit, subjects will be asked to select which SkinMedica products they would like to receive at their final (week 12) visit.

Subjects will be notified of the retail value limits, which cannot be combined, and that the products will be provided, as available. SkinMedica chemical peels will not be eligible. Upon receipt of SkinMedica products, subjects will provide a signature confirming receipt of compensation.

16 STATISTICAL CONSIDERATIONS

16.1 Sample Size

No sample size calculations were performed for this pilot study.

16.2 Analysis Populations

An intent-to-treat (ITT) population will include all subjects who were enrolled and applied the Test Product.

A per-protocol (PP) population will include all subjects who completed all study visits without significant protocol violations. Subjects to be excluded from the PP analysis are subjects who have: 1) no efficacy evaluation at baseline, and/or have no follow-up visit; 2) used any prohibited medications during the study period which would interfere with the study objectives; 3) had any prohibited procedures during the study period which would interfere with the study objectives.

16.3 Statistical Methods

Statistical analyses will be conducted on all subjects who complete at least their baseline visit and subsequent follow-up assessment timepoint. Descriptive statistics (i.e., mean etc.) will be conducted for all subjects who have completed the Baseline and any follow-up visits.

Safety analyses will be performed in terms of incidence and severity adverse events. Concomitant medication/treatment will be listed by subject and study visit.

17 ETHICAL AND REGULATORY CONSIDERATIONS

17.1 Compliance with the Declaration of Helsinki

This study will be conducted in compliance with the principles of the Declaration of Helsinki, with the current Good Clinical Practice (GCP) guideline and with other applicable regulations. The investigator and all study staff will conduct the study in compliance with this protocol. The protocol, informed consent documents, recruitment advertisements and any amendments to these items will have Institutional Review Board (IRB) approval prior to study initiation. Voluntary informed consent will be given by every subject prior to the initiation of any study related procedures. The rights, safety and well-being of the study subjects are the most important considerations and prevail over the interests of science and society. All personnel involved in the conduct of this study must be qualified by education, training and experience to perform their assigned responsibilities.

